1. INTRODUCTION

A human adenovirus-vectored vaccine candidate which has shown promise in preclinical animal models of respiratory syncytial virus (RSV) will be assessed in this study:

- Ad26.RSV.preF (JNJ-64400141), a replication-incompetent adenovirus serotype 26 (Ad26) containing a deoxyribonucleic acid (DNA) transgene that encodes for the pre-fusion conformation-stabilized F protein (pre-F) derived from the RSV A2 strain.

For the most comprehensive nonclinical information regarding Ad26.RSV.preF, refer to the latest version of the Investigator's Brochure for Ad26.RSV.preF.¹

The term "sponsor" used throughout this document refers to the entities listed in the Contact Information page(s), which will be provided as a separate document.

1.1. Background

Background

RSV is an important cause of serious respiratory infections in the elderly, immunocompromised, and those with underlying chronic cardiopulmonary conditions.⁹ Although most adults mount a long-lasting fully protective immune response, waning immune responses in the elderly might contribute to increased susceptibility to severe disease after RSV infection causing significant morbidity and mortality. In long-term care facilities, RSV is estimated to infect 5 to 10% of the residents per year with significant rates of pneumonia (10% to 20%) and death (2% to 5%).¹⁰ In an epidemiology study of RSV burden, it was estimated that 11,000 elderly persons die annually of RSV in the United States (US).²⁸ These data support the importance of developing an effective vaccine for certain adult populations, such as the elderly.

RSV is also considered to be the most important cause of serious acute respiratory illness in infants and children under 5 years of age: worldwide in 2005, RSV caused an estimated 33.8 million new episodes of acute lower respiratory tract infections this age range, with 3.4 million cases requiring hospitalization due to severe illness.^{14,26,27}

Despite the high disease burden, no licensed vaccine is available for RSV. The first vaccine candidate for young children, which consisted of formalin-inactivated RSV (FI-RSV), was associated with enhanced respiratory disease (ERD) upon infection with RSV.¹⁵ Although the mechanisms for ERD are not fully understood, it is thought that FI-RSV failed to induce adequate neutralizing antibody titers and CD8 priming, and induced a T-helper 2 (Th2) skewed response.²²

As all adults have been exposed to RSV, and therefore previously primed by a live virus infection, enhanced disease is not expected to be a concern in this study.⁶

Adenoviral-vectored Vaccines

It is thought that an efficacious RSV vaccine should induce high levels of neutralizing antibodies, CD8⁺ T-cell responses, and Th1-type CD4⁺ T cells.³ The candidate RSV vaccine being evaluated in this protocol is based on the AdVac® platform which has been shown to promote a strong antibody response, as well as CD8⁺ T cell and Th1-type CD4⁺ T-cell responses.

The immunogenicity profile of adenoviral vectors, with particular emphasis on Th1 responses, is illustrated by data obtained from immunization of adults with Ad26-vectored human immunodeficiency virus (HIV) vaccine (Ad26.ENVA.01), and of adults and infants with Ad35-vectored tuberculosis (TB) vaccine (Ad35.TB-S). These data show predominantly interferon gamma (IFN γ) and tumor necrosis factor alpha (TNF α) production in CD4⁺ and CD8⁺ T cells.^{2,5,24} Furthermore, in mice, Ad26- and Ad35-vectored vaccines with circumsporozoite (CS) transgene inserts (Ad26.CS.01 and Ad35.CS.01), when administered as single immunizations or in combination as a heterologous prime-boost regimen at dose levels ranging from 1×10^8 vp (viral particles) to 1×10^{10} vp, induce predominantly CD8⁺ T-cell responses, as well as mainly immunoglobulin IgG2a antibody responses, indicative of a Th1-biased response.²⁵

Ad26.RSV.FA2 Clinical Data

Ad26 encoding for the wild-type RSV FA2 transgene, Ad26.RSV.FA2, has been evaluated in studies VAC18192RSV1001 and VAC18192RSV1003 (N = 48 and 32, respectively, of which 35 and 24 subjects, respectively, received Ad26.RSV.FA2) in adults at doses of 5×10^{10} vp. All subject visits have been completed in both studies.

Results indicate that there have been no safety concerns following vaccination in either study. After vaccination with Ad26.RSV.FA2, local reactogenicity comprised almost exclusively mild to moderate pain of median duration 1 to 3 days. The most commonly experienced solicited systemic adverse events (AEs; headache, fatigue, chills, myalgia) were also mostly mild to moderate and of median duration 1 to 3 days; most unsolicited AEs and most laboratory abnormalities were mild to moderate in severity. No serious adverse events (SAEs) were reported and no AEs led to withdrawal from study vaccine.³¹

Single vaccination with 5×10^{10} vp Ad26.RSV.FA2 raised humoral and cellular immunity. An increase in RSV neutralizing antibody titers was observed; RSV-specific T-cell responses were also increased.

FA2 and preF RSV Vaccines

The candidate vaccine assessed in this study is Ad26.RSV.preF, ie, a replication-incompetent Ad26 containing a DNA transgene that encodes for the pre-fusion conformation-stabilized F protein derived from the RSV A2 strain.

First-in-human clinical studies (VAC18192RSV1001 [first-in-human (FIH) for Ad35.RSV.FA2] and VAC18192RSV1003 [FIH for Ad26.RSV.FA2]) have been completed with vaccines

Ad26.RSV.FA2 and Ad35.RSV.FA2, in which Ad26 and Ad35, respectively, encode for a wild-type RSV F protein of the RSV A2 strain (FA2).

The F protein of RSV undergoes a conformational transition from a metastable pre-fusion conformation to a stable post-fusion conformation. Neutralizing sensitive epitopes reside on both proteins, but recent evidence indicates that those epitopes specific to the pre-F protein seem to be more potent than those present on the post-F protein.^{12,13} This evidence resulted in the design of the candidate RSV vaccine (Ad26.RSV.preF) in which the adenoviral vector encodes for a full length RSV F protein stabilized in the pre-F protein conformation. **CC1**

[REDACTED] This change in the transgene confers more stability to the pre-fusion form of the molecule before it undergoes its natural transition to the post-fusion form.¹⁸ This change also induces higher immune responses against pre-fusion epitopes because the majority of neutralizing antibodies target the pre-fusion protein conformation.^{19,23} For these reasons, it is anticipated that the Ad26.RSV.preF vaccine candidate will generate more neutralizing antibodies relative to the Ad26.RSV.FA2 vaccine.³¹

Ad26.RSV.preF Preclinical Data

Preclinical studies were performed in naïve and RSV pre-exposed animals. Ad26.RSV.preF is immunogenic in mice and cotton rats, with humoral responses that include the induction of RSV neutralizing antibodies. In addition, Ad26.RSV.preF was shown to elicit cellular responses in mice, characterized by the induction of RSV F-specific CD8+ IFN γ + T cells. Single immunization with Ad26.RSV.preF protects cotton rats from challenge with RSV A2 and RSV B strains.³¹

Ad26.RSV.preF Clinical Data

Ad26.RSV.preF is under evaluation in the ongoing FIH Phase 1 study VAC18193RSV1003 in subjects aged ≥ 60 years in stable health. In this randomized, placebo-controlled, double-blind study, 72 male and female subjects were randomized in parallel to 1 of 5 study groups and have received the first (Day 1) of 2 intramuscular injections as follows:

- Group 1 – 5×10^{10} vp Ad26.RSV.preF on Day 1 and 1 year (± 1 month) later;
- Group 2 – 5×10^{10} vp Ad26.RSV.preF on Day 1 and placebo 1 year (± 1 month) later;
- Group 3 – 1×10^{11} vp Ad26.RSV.preF on Day 1 and 1 year (± 1 month) later;
- Group 4 – 1×10^{11} vp Ad26.RSV.preF on Day 1 and placebo 1 year (± 1 month) later;
- Group 5 – placebo on Day 1 and 1 year (± 1 month) later.

Safety and immunogenicity data from the unblinded interim analysis 28 days post-Dose 1 from all 72 subjects who received Ad26.RSV.preF (5×10^{10} vp or 1×10^{11} vp) or placebo confirmed the immunogenicity of the vaccine; the 1×10^{11} vp dose of Ad26.RSV.preF was more immunogenic than the 5×10^{10} vp dose. No safety concerns were revealed; the reactogenicity of both doses was comparable.

For study VAC18193RSV1003, Ad26.RSV.preF was provided in a different buffer (Formulation Buffer 1^a) from the one to be used in the current study (Formulation Buffer 2^b). The formulation buffer was changed to enhance the Ad26.RSV.preF drug product stability at 2 to 8 °C for storage purposes in future studies. The new formulation buffer was considered well-tolerated when tested in a nonclinical single dose intramuscular safety study in rabbits.³¹

Safety Data Supporting Ad26.RSV.preF Dose Selection from Other Ad26-based Vaccines

In addition to the 2 completed studies with Ad26.RSV.FA2 and 1 ongoing study with Ad26.RSV.preF, the dose levels for Ad26.RSV.preF used in this study are supported by experience in adults with other Ad26 vaccines encoding for different antigens (EnvA [in Ad26.ENVA.01 against HIV];^{4,5} CS protein [in Ad26.CS.01 against malaria];^{7,24} and Ebola glycoprotein [in Ad26.ZEBOV against Ebola virus]²¹). Note that, in general, at a given dose level, no significant changes in the safety profiles of Ad26-based vaccines have been seen when the transgene has been changed.

In completed clinical studies, the safety of Ad26.ENVA.01, Ad26.CS.01 and Ad26.RSV.FA2 has previously been evaluated in at least 293 adult subjects, of whom 243 have received 5×10^{10} vp, and found to be well-tolerated. In addition, four Phase 1 studies with Ad26.ZEBOV have been completed in adults: 291 subjects have received Ad26.ZEBOV at 5×10^{10} vp and 1×10^{11} vp without significant safety issues: 15 subjects have received 1×10^{11} vp (25 doses administered), and 276 subjects have received 5×10^{10} vp. The safety data from these Ebola studies showed no safety concerns at 5×10^{10} vp and 1×10^{11} vp. Overall, these clinical data are supportive of dosing Ad26.RSV.preF at 1×10^{11} vp in the current study.

1.2. Seasonal Influenza Vaccine

Fluarix® Quadrivalent (GlaxoSmithKline) is a seasonal, split virion influenza vaccine containing four strains of influenza viruses with 15 µg HA/strain per 0.5 mL dose propagated in embryonated chicken eggs. Fluarix is indicated for active immunization against influenza caused by the specific strains of influenza virus contained in the vaccine in adults and children 3 years of age and older. The vaccine is usually administered intramuscularly by injection into the deltoid muscle.

1.3. Overall Rationale for the Study

Influenza and respiratory syncytial viruses cause infection leading to seasonal illness, hospitalization, morbidity and mortality in the elderly. Influenza vaccines are given yearly before the start of the influenza season and it is likely that an RSV vaccine would be given at the same time, as both RSV and influenza seasons overlap. This study will examine the effect on the safety and immunogenicity of both vaccines of giving a seasonal influenza vaccine and

^a CCI

^b

Ad26.RSV.preF at the same time and at separate times to provide an indication of whether these vaccines can be used concomitantly.

Further discussion on the rationale for the study design is provided in Section [3.2](#).

2. OBJECTIVES, ENDPOINTS, AND HYPOTHESIS

2.1. Objectives and Endpoints

2.1.1. Objectives

Primary Objectives

- To demonstrate the non-inferiority of the concomitant administration of Ad26.RSV.preF and seasonal influenza vaccine versus the administration of seasonal influenza vaccine alone in terms of humoral immune response expressed by the geometric mean titers (GMTs) of hemagglutination inhibition (HI) antibody titers against all four influenza vaccine strains 28 days after the administration of influenza vaccine, using a non-inferiority margin of 2 for the GMT ratio (control group/co-administration group)
- To assess the safety and tolerability of a single dose of 1×10^{11} vp of Ad26.RSV.preF, administered intramuscularly to subjects aged ≥ 60 years separately or concomitantly with seasonal influenza vaccine

Secondary Objectives

- To compare the safety of seasonal influenza vaccine administered separately and concomitantly with Ad26.RSV.preF
- To assess humoral immune responses to RSV after the administration of Ad26.RSV.preF administered separately or concomitantly with seasonal influenza vaccine
- To assess humoral immune responses to influenza after the administration of seasonal influenza vaccine administered separately or concomitantly with Ad26.RSV.preF, in terms of geometric mean fold rises from baseline of HI antibody titers against the four influenza vaccine strains
- Seroconversion rates against the four influenza vaccine strains defined as a post-vaccination titer $\geq 1:40$ in subjects with a pre-vaccination titer of $< 1:10$, or a ≥ 4 -fold titer increase in subjects with a pre-vaccination titer of $\geq 1:10$
- Seroprotection rates against the four influenza vaccine strains defined as the percentage of subjects with a post-vaccination titer $\geq 1:40$

Exploratory Objectives

- To explore the comparison between seasonal influenza vaccine administered separately and concomitantly with Ad26.RSV.preF in terms of cellular responses to RSV F protein (by

enzyme-linked immunospot [ELISpot] assay, flow cytometry) in a limited number of subjects, if feasible

- To explore the comparison between seasonal influenza vaccine administered separately and concomitantly with Ad26.RSV.preF in terms of other immunologic responses to RSV
- To monitor symptoms of respiratory illness via the respiratory tract infection (RTI) symptoms from Day 1 through the end of the study

2.1.2. Endpoints

Primary Endpoints

- HI titers against all four influenza vaccine strains
- Safety and tolerability of Ad26.RSV.preF

Solicited local and systemic AEs for 7 days after each vaccination

Unsolicited AEs from informed consent form (ICF) signature until 28 days after the second vaccination

SAEs from ICF signature throughout the study

Secondary Endpoints

- Safety and tolerability of seasonal influenza vaccine

Solicited local and systemic AEs for 7 days after the first vaccination

Unsolicited AEs from ICF signature until 28 days after the first vaccination

SAEs from ICF signature throughout the study

- Immunogenicity

The analysis of the immunogenicity of the Ad26.RSV.preF and seasonal influenza vaccine will include the characterization of humoral responses.

Humoral Immune Response

- RSV neutralization A2 strain

Analysis of RSV A2 neutralizing titers of the vaccine-induced immune response will be assessed

- RSV F-protein enzyme-linked immunosorbent assay (ELISA; pre- and/or post-fusion F antibodies)

Analysis of antibodies binding to RSV F protein in post-fusion and pre-fusion form

- Hemagglutination inhibition assay (HAI)

Analysis of HI to all the influenza vaccine strains included in the seasonal vaccination

Exploratory Endpoints

- Immunogenicity

Additional exploratory analyses may be performed to investigate vaccine-elicited immune responses further. These may include, but are not limited to, the following assays:

Humoral Immune Response

- RSV cross-neutralization of B and/or other A strain
- F-protein antibody specificity characterization
- Adenovirus neutralization assay
- Functional and molecular antibody characterization
- Influenza virus neutralization assay

Cell-mediated Immune Response to Ad26.RSV.preF and Seasonal Influenza Vaccine

- IFN γ ELISpot cytokine analysis
- Intracellular cytokine staining

Refer to Section [9.2](#) for evaluations related to endpoints.

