Continuous secondary and exploratory variables will be summarized with descriptive statistics of the actual values and the changes from baseline where appropriate. Descriptive statistics (geometric mean and 95% confidence interval for ELISA, virus neutralization and HI assays; median and quartiles for ELISpot and intracellular cytokine staining [ICS]) will be calculated for continuous immunologic parameters at all timepoints. For the humoral assays, geometric mean fold rises from baseline and corresponding 95% confidence intervals might additionally be calculated. For immunogenicity, baseline is considered as the last assessment pre-vaccination. Graphical representations of immunologic parameters will be made as applicable.

Safety Analyses

No formal statistical testing of safety data is planned. For the planned analyses, safety data will be analyzed descriptively by regimen.

TIME AND EVENTS SCHEDULE

Clinic Visit #	1	2 ^a	3	4 ^a	5	6 ^b	Exit ^c
Visit Timing	Vac 1	Vac 1 + 7 d	Vac 2	Vac 2 + 7 d	Vac 2 + 28 d	Vac 2 + 6 mo	
Visit Day	1	8	29	36	57	211	
Visit Window		±2 d	±3 d	±2 d	±3 d	±14 d	
Visit Type	Screening and VACCINATION 1	Safety	VACCINATION 2	Safety	Safety and Immuno.	Safety	Early exit
Written informed consent ^d	●						
Inclusion/exclusion criteria	●						
Demographics	●						
Medical history/pre-study meds	●						
Physical examination ^e	●		●		●		●
Vital signs ^f incl. body temperature	●		●		●		●
12-lead ECG ^g	●						
Randomization	●						
Inclusion/exclusion criteria check ^h			●				
Pre-vaccination symptoms ⁱ	●		●				
Cellular immunity, mL ^j	● 40		● 40		40		● 40
Humoral immunity, mL ^j	● 20		● 20		20		● 20
Vaccination	●		●				
30 minute post-vaccination observation ^k	●		●				
Solicited AE recording	----- 4 -----		----- 4 -----				● 5
Unsolicited AE recording	----- continuous -----						● 6
SAE recording	----- continuous -----						●
Concomitant medications ^l	----- continuous -----						●
RTI ^m	●	----- continuous -----					●
RTI Symptoms Form and nasal turbinate sample kit distribution ⁿ	●						
Subject diary distribution ^o	●		●				
Subject diary review by site staff ^p			●		●		
Approximate daily blood draw, mL (subjects with cellular draw)	60	—	60	—	60	—	60
Approx. cumulative blood draw, mL (subjects with cellular draw)	60	60	120	120	180	180	60

Clinic Visit #	1	2 ^a 	3	4 ^a 	5	6 ^b 	Exit ^c
Visit Timing	Vac 1	Vac 1 + 7 d	Vac 2	Vac 2 + 7 d	Vac 2 + 28 d	Vac 2 + 6 mo	
Visit Day	1	8	29	36	57	211	
Visit Window		±2 d	±3 d	±2 d	±3 d	±14 d	

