3. STUDY DESIGN AND RATIONALE

3.1. Overview of Study Design

This is a single center, randomized, placebo-controlled, double-blind Phase 2a study, to be conducted in 180 adult male and female subjects aged ≥ 60 years of age in stable health randomized in parallel in a 1:1 ratio to one of two groups. Group 1 will receive 1×10^{11} vp Ad26.RSV.preF on Day 1 administered at the same time as a commercially available seasonal influenza vaccine, and placebo on Day 29. Group 2 will receive placebo on Day 1, administered at the same time as a commercially available seasonal influenza vaccine, and 1×10^{11} vp Ad26.RSV.preF on Day 29. All study vaccines will be given by the intramuscular route. An internal data review committee (DRC) will be commissioned for this study.

Table 4: Study Design

Group	N	Day 1	Day 29
1	90	Ad26.RSV.preF (1×10^{11} vp) + Fluarix	Placebo
2	90	Placebo + Fluarix	Ad26.RSV.preF (1×10^{11} vp)

N = number of subjects; vp = viral particles

After each vaccination, subjects will be closely observed for a minimum of 30 minutes post-vaccination to monitor for the development of any acute reactions, or longer if deemed necessary by the investigator. Any unsolicited, solicited local or systemic AEs will be documented by study-site personnel following this observation period. Subjects will be given a thermometer, ruler and daily assessment (subject) diary with instructions for the proper recording of events. Each subject will record solicited local (at injection site) and systemic AEs and body temperatures, beginning on the evening of each study vaccine dosing day and on a daily basis for the following 7 days. Body temperatures should be taken at approximately the same time each day. Study-site personnel will collect and review subject diary information and confirm the entries at subsequent site visits.

Unsolicited AEs will be collected from ICF signature through 28 days after the second vaccination. SAEs will be collected from ICF signature until the end of the study. All AEs, including any that are ongoing 28 days after the second vaccination, will be followed until clinical resolution or stabilization. Concomitant medications will be collected and recorded in the electronic case report form (eCRF) from the time of first vaccination through 28 days after the second vaccination, and additionally outside of this period when associated with an SAE.

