Blood will be collected from all subjects to assess humoral immune responses pre-vaccination on each dosing day, and at 28 days after the second vaccination (or at the early exit visit if the subject prematurely terminates the study before Day 57 without withdrawing consent^a); cellular immune responses may be assessed at these timepoints in a subset containing 40 randomized subjects (ie, 20 per group).

^a Immunogenicity blood samples will only be taken if early exit is at least 14 days after the previous immunogenicity blood draw.

[figure not shown]
An independent unblinded statistician and unblinded biomarker representative will present data to the DRC if non-inferiority of the concomitant administration of influenza vaccine with Ad26.RSV.preF versus the administration of influenza vaccine alone is not demonstrated, based on the immunogenicity analysis at 28 days after the first dose. The DRC will decide if subjects should be offered repeat influenza immunization (see Section 11.6 for more details).

The study duration will be approximately 30 weeks per participant. The study comprises vaccination for each subject on Day 1 and Day 29, a 28-day follow-up period after each vaccination, and a follow-up until 6 months after the second vaccination. The end of the study will be the last subject's last visit by telephone at 6 months after the second vaccination.

If symptoms of an RTI develop from Day 1 through the end of the study, subjects should record signs and symptoms of the RTI using a specific RTI Symptoms Form and, if feasible, take a nasal turbinate sample. Details on procedures in the event of an RTI are described in Section 9.2.3.

Unscheduled study visits may be performed based on investigator's clinical judgment and may include further evaluations, as needed.

A diagram of the entire study design is provided in [Figure 1](#).

Figure 1: Schematic Overview of the Study

*by telephone

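### The SAE part of the Fluarix safety endpoint runs past Day 29, so over the whole study it compares two regimens that both contain Ad26.RSV.preF

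*Protocol*

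**What the plan says.** The secondary safety objective in section 2.1.1 is "To compare the safety of seasonal influenza vaccine administered separately and concomitantly with Ad26.RSV.preF". Section 2.1.2 gives the matching endpoint three parts, and the synopsis repeats them:

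- Diary events: "Solicited local and systemic AEs for 7 days after the first vaccination"
- Events outside the diary: "Unsolicited AEs from ICF signature until 28 days after the first vaccination"
- Serious events: "SAEs from ICF signature throughout the study"

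The SAE line is worded identically in the primary Ad26.RSV.preF safety endpoint. The other two lines were shortened from their primary counterparts, which cover both vaccinations.

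Under section 3.1 and Table 4, Group 1 (CoAd) receives Ad26.RSV.preF with Fluarix on Day 1 and placebo on Day 29. Group 2 (Control) receives placebo with Fluarix on Day 1 and 1 × 10¹¹ "vp Ad26.RSV.preF on Day 29". The Time and Events Schedule gives "Visit Day 1 8 29 36 57 211". Section 3.1 describes "a follow-up until 6 months after the second vaccination" and adds: "The study duration will be approximately 30 weeks per participant".

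Section 11.5 makes the safety analysis descriptive, by regimen. It limits AEs to onset within 28 days of a vaccination but takes in every SAE, with no split at the second vaccination.

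**The concern.** Until the second injection the groups differ in one respect: CoAd has had Ad26.RSV.preF with Fluarix, and Control has had Fluarix with placebo. From Day 29 that difference is gone, because both groups have had Fluarix and one dose of Ad26.RSV.preF, differing only in timing. Two of the endpoint's three parts respect this boundary and the SAE part does not.

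At stake is what the SAE summary can show. If Ad26.RSV.preF raises SAE risk for a while after it is given, the excess appears early in CoAd and after Day 29 in Control, and the two cancel in whole-study totals. If the excess arises only with co-administration, it survives but is diluted by the much longer later follow-up.

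**Working it through.** **Inputs.** First vaccination Day 1, second Day 29, final visit Day 211 (Time and Events Schedule). Windows of ±3 days for the second vaccination and ±14 days for the final visit (section 9.1.2). Illness delay of up to 10 days (section 9.1.4). 90 subjects per group (Table 4). Consent, screening and first vaccination are all planned for Day 1 (section 4 and the schedule), so pre-dose time is taken as nil.

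**Plan's own figure.** (211 − 1)/7 = 210/7 = 30.0 weeks, which matches the stated duration.

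**Share of Control's SAE time after Ad26.RSV.preF.**

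- Nominal: (211 − 29)/(211 − 1) = 182/210 = 86.7%. The remaining 28/210 = 13.3% precedes it.
- Within windows: second vaccination on Day 26 to 32, final visit 168 to 196 days later. Lowest 168/(32 + 168 − 1) = 168/199 = 84.4%; highest 196/(26 + 196 − 1) = 196/221 = 88.7%.
- With a 10-day delay (Day 39): 168/206 = 81.6% to 196/234 = 83.8%.
- Person-time for 90 subjects: 90 × 28/365.25 = 6.9 person-years before, and 90 × 182/365.25 = 44.8 after.

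These figures assume that Control subjects receive the second injection and complete follow-up.

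**Effect on a group ratio (illustration).** Take a constant background SAE rate, multiplied by r for 28 days after the relevant dose. Both r and the 28 days are assumptions.

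- *Excess after Ad26.RSV.preF whenever it is given.* The ratio over the first 28 days is r. Over the whole study, CoAd has 28r + 182 and Control has 28 + 28r + 154 = 28r + 182. The ratio is 1.0 for every r.
- *Excess only with co-administration.* The whole-study ratio is (28r + 182)/210. For r = 2, 3 and 5 this gives 238/210 = 1.13, 266/210 = 1.27 and 322/210 = 1.53.

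**Expected events per group.** The protocol gives no SAE rate, so the rate below is assumed constant, with a range.

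| Assumed rate per 30 days | First 28 days | Whole 210 days |
|---|---|---|
| 0.5% | 90 × 0.005 × 28/30 = 0.42 | 90 × 0.005 × 210/30 = 3.15 |
| 1% | 90 × 0.01 × 28/30 = 0.84 | 90 × 0.01 × 210/30 = 6.3 |
| 2% | 90 × 0.02 × 28/30 = 1.68 | 90 × 0.02 × 210/30 = 12.6 |

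The ratio of the two columns, 210/28 = 7.5, holds at any constant rate.

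**What early SAEs the endpoint already shows.** Section 12 defines unsolicited AEs as those not asked about in the diary and does not exclude serious ones. Section 12.1.1 treats SAEs as untoward medical occurrences that meet a seriousness criterion. A non-diary SAE in the first 28 days therefore also counts in the unsolicited part. That part does not separate serious from non-serious events, and a diary-type event that becomes serious falls outside it.

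**The case against.** The strongest defence is that the objective says separately, not alone. Sections 1.3 and 3.2 describe the question as giving the two vaccines together or at different times. On that reading Control is the sequential regimen, and whole-study SAEs by regimen compare what was intended. This stands as far as it goes: the whole-study summary is a valid comparison of regimens and should be kept. It does not explain why the other two parts of the endpoint stop before or at the second vaccination, and the primary Ad26.RSV.preF endpoint already supplies the whole-study SAE window.

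A reader might infer that SAEs occurring in Control after Day 29 will be reported as SAEs of Fluarix alone. The protocol does not support that. No section sets up such a table; section 11.5 summarizes by group and allows SAE listings and narratives; onset dates permit a split; and section 12.1.2 requires a causality judgement for every AE. Nor does it follow that later SAEs should be discarded. In CoAd, which receives only placebo on Day 29, a late SAE may still bear on co-administration.

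It is also fair to say that safety is descriptive, that the first period will hold very few events, and that section 11 leaves detail to the SAP, which may split by period. The first two points limit the weight of the concern. On the third, the endpoint window is stated in the protocol itself, so the protocol wording is the place to correct it.

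**Conclusion.** The point holds in limited form. The SAE part of the Fluarix endpoint is out of line with the other two parts, and over the whole study it cannot by itself show the contrast before Control receives Ad26.RSV.preF. The share of Control's SAE time affected follows from the protocol's schedule alone. The group ratios rest on an assumed risk pattern, and the event counts on an assumed SAE rate. SAE collection to the end of the study is not at fault. The correction is worth making because it is cheap and makes the endpoint internally consistent, but no formal test, sample size statement or pausing rule depends on it.

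**What to change.** In section 2.1.2 and the synopsis, state that the Fluarix SAE comparison is made on SAEs with onset from the first vaccination until the second injection, or until 28 days after the first vaccination if the second is not given. Keep the whole-study SAE summary by regimen, and show later SAEs separately by regimen. Leave SAE collection through 6 months after the second vaccination as it is.

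The cost is one change of endpoint wording and one split of the SAE table by onset date, using data already collected. The drawback is the small number of events in the first period, so the text should say that this comparison is descriptive and that few or no events there is not evidence of equal risk. With a delayed second injection the period runs somewhat beyond 28 days, so the summary should give follow-up time per group.
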